In our preliminary study (unpublished) with limited sample size, we compared two different bone marrow samples (CD138 selected DNA extract vs. formalin-fixed paraffin embedded (FFPE) bone marrow clot section) from same patients (from Moffitt Cancer Center) and demonstrated that high-throughput sequencing technology by Adaptive Biotechnologies can identify the index myeloma clones (data not shown). We hypothesize that high-throughput sequencing technology using PCR on CDR3 sequences will identify minimal residual disease in myeloma patients after autologous HCT followed by panobinostat maintenance and bone marrow samples will be obtained prospectively to analyze this technology.

3 Study rationale/purpose

Optimal maintenance therapy after autologous HCT in multiple myeloma has not been defined. Based on preclinical and clinical data demonstrating anti-myeloma activity of panobinostat, we propose an open-label, trial to determine the safety and tolerability of 2 dosing schedules of panobinostat maintenance therapy in patients with multiple myeloma who underwent autologous HCT. As noted in prior maintenance therapy in myeloma, the dose of maintenance single agent is usually started at a lower dose (such as 10 mg starting dose for lenalidomide maintenance compared to 25 mg full dose in relapsed/refractory disease treatment) due primarily to (1) lower disease burden after autologous HCT and (2) limited tolerability and susceptibility to cytopenias immediately after autologous HCT. Panobinostat maintenance therapy will be initiated between 90 days and 180 days after autologous HCT at a starting dose of (a) 20 mg PO three times a week, every other week, every 4 weeks (Cohort A), or (b) 10 mg po daily x 7 days, every other week, every 4 weeks (Cohort B). Maintenance therapy will be prescribed for a maximum for 12 cycles (4 weeks x 12 cycles = 48 weeks) for both cohorts. The dose delivered to each cohort would be 60 mg per week for Cohort A and 70 mg per week for Cohort B. Long-term tolerability of each dose schedule of panobinostat

maintenance therapy after autologous HCT is unknown and the study intends to evaluate the safety and tolerability in multiple myeloma patients.

4 Study objectives

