7.3 Treatment cycle and duration

One treatment cycle consists of oral panobinostat either (1) 20 mg PO three times per week, every other week, of a 28-day schedule, or (2) 10 mg PO daily x 7 days, every other week, of a 28-day schedule. Patients may continue treatment with oral panobinostat until they experience unacceptable toxicity that precludes further treatment, disease progression, and/or at the discretion of the investigator. The planned treatment is for a total of 12 cycles (48 weeks).

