7.4.1 Dose reduction for panobinostat

This is an open-label trial to determine the safety and tolerability of single agent panobinostat (2 dosing schedules) as maintenance therapy after autologous HCT in patients with multiple myeloma. Patients will receive either 20 mg PO TIW, every other week, every 28-days (Cohort A) or 10 mg po daily x 7 days, every other week, every 4 weeks (Cohort B). If no grade 3 or 4 toxicities occur after completing a 28-day cycle of panobinostat maintenance therapy, and all non-hematologic toxicities improved to grade 1 or better, then the next cycle of panobinostat will be initiated as long as the minimal hematologic parameters are met (ANC $\geq 1 \times 10^9/L$; hemoglobin ≥ 8 g/dl; platelets $50 \times 10^9/L$) prior to each cycle. If a subject experiences toxicity, the dose of panobinostat will be reduced to one level lower (Table 7-1) and maintained at this level for all subsequent cycles unless further toxicities occur. Panobinostat dose modifications will be made according to the toxicity grading. Once a subject's dose of panobinostat is reduced, then that dose will be the maximal dose administered. The provisional dose levels of panobinostat (LBH589) to be investigated in this study are described in Table 7-1.

Table 7-1 Provisional dose reduction for panobinostat (LBH589)

Dose level#	Panobinostat oral dose	
	Cohort A (TIW, every other week, every 4 weeks)	Cohort B (Daily x 7 days, every other week, every 4 weeks)
1 (starting dose level)	20 mg	10 mg
-1	15 mg	10 mg on days 1, 3, 5, and 7

7.4.2 Dose modifications for study drug-related toxicity (see section 7.4.3 for dose modifications for prolonged QTc):

The criteria for dose modifications for study drug-related toxicity are detailed in [Table 7-2](#).

Table 7-2 Criteria for dosing delays, dose-reductions, and re-initiation of treatment due to study drug-related toxicity (excluding QT prolongation)

Worst Toxicity CTCAE Grade* unless otherwise specified (Value)	Dose Modification Guidelines At any time during a cycle of therapy (including intended day of dosing)	
HEMATOLOGICAL TOXICITIES		
Thrombocytopenia	Grade 3 (<50 and $\geq 25 \times 10^9/L$) with bleeding and Grade 4 (< $25 \times 10^9/L$)	Temporarily discontinue panobinostat dosing until resolved to \leq grade 2, or baseline, then, restart panobinostat at reduced level as per Table 7-1

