7.4.5 Follow-up for toxicities

Patients whose treatment is interrupted or permanently discontinued due to an adverse event or abnormal laboratory value must be followed until resolution or stabilization of the event, whichever comes first.

If a patient requires a dose delay of > 28 days from the intended day of the next scheduled dose, then the patient must be discontinued from the study. If however the patient was clearly benefiting from panobinostat therapy, the patient may be able to continue treatment with a dose reduction at the Investigator discretion, after resolution of the adverse event. All patients will be followed for adverse events and serious adverse events for at least 4 weeks following the last dose of oral panobinostat.

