8.1 Visit schedule

Table 8-1 Evaluation and visit schedule

	Pre-HCT (Screening, not required)	Prior to maintenance (Enrollment: +45 to +180) [§]	Cycle #1 (start between +90 and +180)	Cycle #2****	Cycle #3****	Cycle #4****	Cycle #5****	Cycle #6****	Cycle #7****	Cycle #8****	Cycle #9****	Cycle #10*** *	Cycle #11*** *	Cycle #12*** *	End of study visit (4 weeks (± 14 days) follow up after the first dose of cycle #12)
Consent	X ⁺	X													
Enrollment		X													
H&P (SOC)		X	X ^{SS§}	X	X	X	X	X	X	X	X	X	X	X	X
Concomitant medications		X													
Toxicity (adverse event (AE)) assessment ^{SS}			X	X	X	X	X	X	X	X	X	X	X	X	X
Vital signs (SOC)		X ⁺⁺	X	X	X	X	X	X	X	X	X	X	X	X	X
EKG		X	X [*]	X ^{**}	X ^{**}	X ^{**}									
CBC and CMP (SOC)		X	X ^{***}	X ^{***}	X	X	X	X	X	X	X	X	X	X	X
PT/INR/PTT		X			X			X							X
LDH, cholesterol panel, GGT, uric acid		X													
Urinalysis		X													X
TSH, free T4		X													X
Serum pregnancy test ⁺⁺⁺		X	X	X	X	X	X	X	X	X	X	X	X	X	
SPEP, UPEP and serum free		X			X			X			X			X	

Confidential

light chains (SOC)															
Pneumococcal-13 conjugate vaccine (at around day +90 – SOC)		X [#]													
Peripheral blood research samples	X	X	X ^{****}	X	X			X			X				X
Bone marrow research samples	X [@]	X													X
Stem cell graft research samples	X														

*Single 12 lead EKG will be performed for pre-dose and 3 hours (± 15 minutes) post-dose on days 1 and 5 of cycle 1. A total of 4 EKGs during cycle 1 will be performed.
 **Single 12 lead EKG will be performed for pre-dose on day 1 of cycle 2 and beyond at each cycle (at least through cycle 4). If no significant QTcF prolongation is noted during the first cycle, then QTc monitoring is no longer required beyond cycle 4 (and may be performed at the investigator’s discretion). One EKG per cycle from cycle 2 to 4 (minimum).
 ***CBC to be performed weekly during cycle #1 and #2. CBC/CMP will also be performed on day 5 of cycle 1.
 ****Window to start cycles #2 to #12 would be ±7 days from the planned first day of each cycle.
 + Screening consent for research samples (bone marrow, peripheral blood and stem cell graft)
 ++ Height will be measured at screening visit prior to starting panobinostat maintenance therapy
 +++ Only for women of child bearing potential
 ++++ Peripheral blood research samples will be also collected on day 5 of cycle 1.

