8.3.4 Laboratory evaluations

Laboratory evaluation should be done at baseline (within ≤ 72 hours prior to dosing prior to the first administration of oral LBH589), during the course of the study and at the time of the study treatment completion visit. Results must be reviewed prior to administering LBH589. More frequent examinations may be performed if medically indicated; results should be recorded.

Hematology

Hematology must include hemoglobin, hematocrit, platelets, total white blood cell count (WBC) and differential. The coagulation profile includes a prothrombin time or International Normalized Ratio (INR), activated partial thromboplastin time and fibrinogen.

Blood chemistry

Biochemistry includes the following parameters: BUN, creatinine, sodium, potassium, chloride, CO₂ (HCO₃), glucose, calcium, albumin, total protein, total bilirubin, alkaline phosphatase, LDH, AST/SGOT, ALT/SGPT, phosphorous, magnesium. If total bilirubin is greater than the upper limit of normal, direct and indirect bilirubin may be performed. Biochemistry tests should be obtained after patient has fasted, if possible.

Urinalysis

Standard urinalysis dipstick assessment (pH, protein, glucose, blood, ketones, and leukocytes) should be performed. This must be supplemented with laboratory quantification of any potentially relevant abnormalities.

Thyroid function test

Thyroid Stimulating Hormone (TSH) and free T4 (thyroxine) will be measured at baseline and at study treatment completion.

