10.1.2 Reporting

All SAEs will be reported as assessed by the investigator. SAEs will be followed until resolution or until clinically relevant improvement or stabilization.

To ensure patient safety, every SAE with suspected causality, occurring after the patient has provided informed consent and until at least 30 days after the patient has stopped study treatment must be reported to Novartis within 24 hours of learning of its occurrence.

Any SAEs experienced after this 30 days period should only be reported to Novartis if the investigator suspects a causal relationship to the study treatment. Recurrent episodes, complications, or progression of the initial SAE must be reported as follow-up to the original episode within 24 hours of the investigator receiving the follow-up information. An SAE occurring at a different time interval or otherwise considered completely unrelated to a previously reported one should be reported separately as a new event.

Information about all SAEs is collected and recorded on the Serious Adverse Event Report Form as outlined per contractual agreement; all applicable sections of the form must be completed in order to provide a clinically thorough report. The investigator must assess and record the relationship of each SAE to each specific study treatment (if there is more than one study treatment), complete the SAE Report Form in English, and send the completed, signed form by fax within 24 hours to the oncology Novartis Drug Safety and Epidemiology (DS&E) department.

The telephone and telefax number of the contact persons in the local department of Drug Safety and Epidemiology (DS&E) are included in the contractual agreement. The original

copy of the SAE Report Form and the fax confirmation sheet should be kept with the case report form documentation at the study site.

Follow-up information is sent to the same contact(s) to whom the original SAE Report Form was sent, using a new SAE Report Form stating that this is a follow-up to the previously reported SAE and giving the date of the original report. Each re-occurrence, complication, or progression of the original event should be reported as a follow-up to that event regardless of when it occurs. The follow-up information should describe whether the event has resolved or continues, if and how it was treated, whether the blind was broken or not, and whether the patient continued or withdrew from study participation.

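### The end-of-study visit is timed from the first dose of cycle 12, so for a fully dosed patient it falls short of the 4-week and 30-day post-last-dose safety periods, and early stoppers have no such visit

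*Combined protocol and SAP*

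**What the plan says.** The visit schedule (section 8.1, Table 8-1) has one column after cycle 12: "End of study visit (4 weeks (± 14 days) follow up after the first dose of cycle #12". It carries the final toxicity assessment, history and physical, blood counts and chemistry, coagulation, urinalysis, thyroid tests, and the last blood and marrow research samples.

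Three other sections bear on what should happen after treatment:

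- Section 7.4.5: "All patients will be followed for adverse events and serious adverse events for at least 4 weeks following the last dose of oral panobinostat".
- Section 10.1.2: serious events with suspected causality, from consent "until at least 30 days after the patient has stopped study treatment must be reported to Novartis".
- Section 8.3.4: laboratory tests at baseline, "during the course of the study and at the time of the study treatment completion visit". That visit is given no date and has no column of its own in Table 8-1.

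Section 7.3 gives the dosing pattern as "20 mg PO three times per week, every other week, of a 28-day schedule" for Cohort A and "10 mg PO daily x 7 days, every other week, of a 28-day schedule" for Cohort B. Section 8.3 ties the cycle visits to day 1 of each cycle and ends them at progression or unacceptable toxicity.

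**The concern.** The follow-up periods in sections 7.4.5 and 10.1.2 run from the end of treatment. The visit runs from the start of the last cycle. Because drug is still planned in the second active week of cycle 12, the two clocks differ by more than two weeks, and the visit window is not wide enough to absorb the difference. A patient who stops in an earlier cycle has no first dose of cycle 12, so the column has no date for that patient.

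The safety profile is part of the primary objective (sections 4.1 and 13.1.3). Section 13.1 plans to report the incidence of grade 3 or higher toxicity, and section 13.1.5 suspends accrual if the non-hematologic grade 3 or 4 rate reaches 40%. Section 8.3.1 has adverse events sought by questioning at each visit, and no visit or call is scheduled after this one. Events that appear late, or after an early stop, depend on unscheduled contact. With 15 patients per cohort, one patient whose event goes unrecorded moves a cohort rate by 1/15 = 6.7 percentage points.

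**Working it through.** **Inputs.** The visit is 28 ± 14 days after the first dose of cycle 12, so 14, 28 or 42 days after it (earliest, nominal, latest; Table 8-1). The targets are 28 days (7.4.5) and 30 days (10.1.2) after the last dose. Dosing days come from sections 7.3 and 7.4.1.

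**The plan's own figures.** 12 × 28 = 336 days = 48 weeks, as section 7.3 states. Per active week, 3 × 20 = 60 mg and 7 × 10 = 70 mg. This matches "60 mg per week for Cohort A and 70 mg per week for Cohort B" in section 3 and confirms three and seven dosing days per active week.

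**Offset from first to last dose of cycle 12.**
- Cohort B: days 1–7 and 15–21, so 21 − 1 = 20 days. At the reduced level ("10 mg on days 1, 3, 5, and 7") the last dosing day of the active week is still day 7, so the offset is still 20.
- Cohort A: the schedule figure is not shown, so I assume days 1, 3, 5, 15, 17 and 19. The ECGs before and after dosing on days 1 and 5 of cycle 1 fit this. The offset is 19 − 1 = 18 days. With the first dose on day 1, any three days in the second active week give 16 to 20.

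**Days from last dose to visit** = visit day after first dose − offset.

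| Pattern | Offset | Earliest | Nominal | Latest | Short of 28 | Short of 30 |
|---|---|---|---|---|---|---|
| A, days 1/3/5/15/17/19 | 18 | −4 | 10 | 24 | 4 | 6 |
| A, second week ends as early as possible | 16 | −2 | 12 | 26 | 2 | 4 |
| A, second week ends as late as possible | 20 | −6 | 8 | 22 | 6 | 8 |
| B, full or reduced level | 20 | −6 | 8 | 22 | 6 | 8 |

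A negative value means that the visit precedes the last planned dose. The last two columns are shortfalls at the latest permitted visit. If the active weeks are 2 and 4 instead of 1 and 3, nothing changes, because the anchor is the first dose.

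**What would be needed.** To reach 28 days, the visit must be at least 18 + 28 = 46 days (A) or 20 + 28 = 48 days (B) after the first cycle-12 dose; for 30 days, 48 or 50. The window closes at 42.

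**Where the shortfall disappears.** If the whole second active week is omitted, the offset is 4 (A) or 6 (B), and the latest visit is 42 − 4 = 38 or 42 − 6 = 36 days after the last dose, beyond both periods. If only the day-15 dose of that week is taken, the latest visit is 42 − 14 = 28 days, which just meets 4 weeks but not 30 days. Doses delayed within cycle 12 lengthen the offset and shorten the gap.

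**Patients without the anchor.** If exactly two-thirds complete, as section 13.1.3 hypothesizes at minimum, 15 × 1/3 = 5 per cohort, or 10 of 30, do not complete. Those who stop before cycle 12 have no end-of-study date. The number needing one is at most 10 on this assumption, since some may have died or may stop within cycle 12. Replaced patients (section 13.1) would add to it.

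**The case against.** The strongest reply is that the protocol does not rely on Table 8-1 for follow-up. Section 7.4.5 covers all patients. It also requires that anyone whose treatment is interrupted or ended by an adverse event or abnormal laboratory value be followed until that event settles. Section 8.3.1 accepts events reported between visits, and section 8.3.4 asks for laboratory and thyroid tests at treatment completion without tying them to cycle 12. Nothing in the table says that event collection closes at the end-of-study visit.

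This stands as far as it goes. A reader might infer that early stoppers have no follow-up, or that late events will be lost. The documents do not support either: the duty exists, and under-ascertainment is a risk, not something shown. The reply does not remove the gap, however. Following a known event to resolution does not find new ones, and the completion visit in 8.3.4 has no date.

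A reader might also infer that the 4-week and 30-day periods contradict each other. They do not. One is a minimum for adverse-event follow-up, and the other governs reporting of serious events to the supporting company, which continues beyond 30 days where causality is suspected.

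Finally, moving the whole end-of-study column would have a cost. It also carries the final blood and marrow research samples, including the acetylation and HDAC-activity samples that section 9.1 places after completion of maintenance.

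**Conclusion.** The point holds for a patient who takes cycle 12 as scheduled. The only post-treatment visit falls 8 to 10 days after the last dose, may be held before the last doses are taken, and at its latest is 24 (A) or 22 (B) days after the last dose, and at most 26 for any Cohort A day pattern. It reaches neither 28 nor 30 days. The Cohort B result needs no assumption about weekdays. The 18-day offset for Cohort A does, but the conclusion survives every pattern that starts on day 1.

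It would go too far to say that the visit can never reach those periods: the late limit reaches both if the second active week of cycle 12 is wholly omitted. It would also go too far to say that the primary endpoint is compromised. The 12-cycle completion rate and relative dose intensity do not depend on this visit. What is exposed is the safety part of the primary objective, through events after the last dose and in patients who stop early. The size of any loss cannot be estimated from the documents.

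**What to change.** Reconcile Table 8-1 with sections 7.4.5, 8.3.4 and 10.1.2:

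- Anchor the final adverse-event and serious-adverse-event assessment to the last dose of panobinostat actually taken, for every patient and whatever the reason for stopping.
- Give it a bounded window that opens no earlier than the protocol's own follow-up periods, for example 30 to 44 days after the last dose. Re-anchoring while keeping ± 14 days around 4 weeks would not be enough, because it would still allow a visit 28 − 14 = 14 days after the last dose.
- State when the treatment-completion visit in section 8.3.4 takes place, and for whom.
- Leave the end-of-study research blood and marrow samples at their present timing, and do not extend marrow sampling to early stoppers through this change.

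The cost is a short amendment and one extra safety contact per patient, by clinic visit or call. If the sponsor instead moves the safety items of the existing visit, completers have their closing assessment about 3 weeks later (30 − 10 = 20 days in Cohort A, 30 − 8 = 22 in Cohort B), separate from the research sampling.

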7.1 Investigational therapy

[figure not shown]
Screening consents will be signed prior to autologous HCT to access pre-HCT stem cell graft, bone marrow and peripheral blood samples for the correlative studies. Patients will be enrolled after autologous HCT. Patients will be initiated on panobinostat maintenance therapy between day +90 and +180 after autologous HCT. Patients who develop disease progression before day +90 after autologous HCT will be ineligible for the study.

Panobinostat (also known as LBH589) will be provided by Novartis. Oral panobinostat will be supplied as 5-mg, 10-mg, 15-mg or 20-mg pink/opaque-colored, hard gelatin capsules.

Medication labels will comply with US legal requirements and be printed in English. They will supply no information about the patient. The storage conditions for study drug will be described on the medication label.

During the study, panobinostat will be administered orally as either (1) once daily dose of 20 mg (1 x 20-mg capsule) three times per week, every other week, of a 28-day schedule (Cohort A), or (2) once daily dose of 10 mg (1 x 10-mg capsule) daily x 7 days, every other week, of a 28-day schedule (Cohort B). Both cohorts will receive a maximum of 12 cycles of maintenance therapy (Figure 7-1).

Figure 7-1. Panobinostat maintenance schedule

Patients should be instructed to take their once-a-day oral dose of panobinostat at the same time each morning. Each dose of panobinostat should be taken with an 8 oz / 240 ml glass of water. Patients should be instructed to swallow the capsules whole and not chew them. Patients must avoid grapefruit or grapefruit juice and seville (sour) oranges during the entire study.

If a subject experiences toxicity, the dose of panobinostat will be reduced to one level lower (Table 7-1) and maintained at this level for all subsequent cycles unless further toxicities occur. Panobinostat dose modifications will be made according to the toxicity grading. Once a subject's dose of panobinostat is reduced, then that dose will be the maximal dose administered.

On the days of ECG monitoring, drug administration should be supervised by study center personnel and administration time should be recorded.

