8.3 Safety assessments

Safety assessments will consist of monitoring and recording unexpected grades ≥ 3 adverse events and serious adverse events, the regular monitoring of hematology, blood chemistry and urine values, vital signs, ECOG performance status, and the regular physical examinations and ECG assessments. All patients will be seen on day 1 of each cycle throughout the maintenance therapy until disease progression or unacceptable toxicities occur (Table 8-1). Additional evaluations may be performed if clinically indicated.

Adverse events will be assessed according to the Common Toxicity Criteria for Adverse Events (CTCAE) version 4.03. CTCAE v4.0 can be accessed on the NIH/NCI website at (http://evs.nci.nih.gov/ftp1/CTCAE/CTCAE_4.03_2010-06-14_QuickReference_5x7.pdf)

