13.1 Statistical methods and data analysis

This is an open label study of 2 different panobinostat maintenance dosing schedules after autologous HCT in patients with multiple myeloma. There are 2 cohorts and patients will be enrolled sequentially to cohort A, then to cohort B. The sample size is 30 patients for this trial (15 for each cohort). We expect that at least 2/3 of each cohort will complete 12 cycles of maintenance panobinostat (regardless of dose modification) and will be evaluable for the primary endpoint. The widths of 95% confidence interval (CI) are 0.356, 0.438, 0.487, 0.514, and 0.522 when the proportions of patients tolerating 12 cycles of maintenance are 0.9, 0.8, 0.7, 0.6, and 0.5, respectively.

A patient who withdraws from the study due to reasons other than death, disease progression or toxicity will be replaced and is considered as non-evaluable for primary endpoint. The proportion of patients tolerating the therapy will be reported with 95% CI. All 30 patients are eligible for secondary endpoints. We will compute the overall response rates before the transplant, after autologous HCT, and after the completion of maintenance therapy, and at best response. The OS and PFS will be estimated using the Kaplan-Meier method. We will also report the incidences of all grades and grade ≥ 3 toxicities. The two-sided 95% CIs for

proportion, and OS and PFS will be computed using the Clopper-Pearson method and the Greenwood formula, respectively. In addition, the frequency of B cell precursor as well as other cell subsets, and their 95% CI will be evaluated using t-distribution. If data do not meet normality assumption, the power transformation (e.g., log-transformation) will be conducted. Those patients who are not in CR before the transplant would be most suitable for T-effector activity analysis. This will be examined by the paired t-test or the Wilcoxon signed-rank test, depending on the data distribution.

Relative dose intensity (RDI) represents the ratio of the amount of a drug actually delivered [actual dose intensity (DI)] to the amount planned (planned DI). The purpose of calculating RDI is to evaluate whether the planned DI of a chemotherapy treatment was actually achieved which may suggest the feasibility of planned treatment regimen. There are multitude of reports demonstrating a correlation between RDI and survival in cancer treatment.

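### After cycle 2 the only scheduled blood count is at the start of each cycle, so late-onset and per-cycle hematologic toxicity is likely understated by an unknown amount and should be tabulated separately

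*Combined protocol and SAP*

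**What the plan says.** The footnote to the CBC/CMP row of Table 8-1 (Section 8.1) reads "CBC to be performed weekly during cycle #1 and #2", and adds "CBC/CMP will also be performed on day 5 of cycle 1". The entries for cycles 3 to 12 carry no footnote: one mark per cycle. Section 8.3 fixes the day: "All patients will be seen on day 1 of each cycle throughout the maintenance therapy". Section 7.4.1 is consistent with this, since a new cycle starts only "as long as the minimal hematologic parameters are met".

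Both cohorts take panobinostat every other week of a 28-day cycle, for up to 12 cycles (Sections 7.1 and 7.3). Cycles 2 to 12 may start up to 7 days either side of the planned date (Table 8-1). Section 8.3.4 permits extra laboratory tests when medically indicated and asks for their results to be recorded.

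Table 7-2 sets hematologic dose modification to act "At any time during a cycle of therapy (including intended day of dosing". Section 13.1 states "We will also report the incidences of all grades" and of grade 3 or higher, with no breakdown by cycle or by count frequency. The safety profile is part of the primary objective (Section 4.1), and Section 3 names long-term tolerability as the unknown that the study addresses.

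**The concern.** The frequency of blood counts drops sharply after cycle 2, and the remaining count comes at the end of a drug-free week. Cycles 3 to 12 are the long-term part of the trial. If low counts appear during or soon after a dosing week and have recovered by the next day 1, the schedule does not see them. A report that sets late cycles beside early ones would then show toxicity falling after cycle 2 partly because fewer counts were taken. A reader could take that as good late tolerability. Section 3 itself gives susceptibility to cytopenias after transplant as a reason for the low starting dose, so this is a toxicity on which the report should be clear.

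There is also a question of consistency. Table 7-2 acts on platelets and neutrophils at any point in the cycle, yet from cycle 3 no count is scheduled between one day 1 and the next. The second dosing week of each such cycle begins on a scheduled count that is nominally 14 days old.

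**Working it through.** **The plan's own figure.** The only precision figures given are the five 95% CI widths for the completion proportion (Section 13.1). Clopper–Pearson limits with n = 15 and x = 15p give 0.3561, 0.4376, 0.4868, 0.5138 and 0.5224 at p = 0.9, 0.8, 0.7, 0.6 and 0.5. These match the stated 0.356, 0.438, 0.487, 0.514 and 0.522. They do not depend on the count schedule, so this point leaves them untouched.

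**Number of scheduled counts (Table 8-1).** Cycle 1: 4 weekly + day 5 = 5. Cycle 2: 4. Cycles 3 to 12: 10 × 1 = 10. End of study: 1. Total 5 + 4 + 10 + 1 = 20. One scheduled count per cycle applies to 10 of 12 cycles (83%).

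**Gap from last dose to the next day-1 count.** Assumption: dosing weeks are 1 and 3 (Figure 7-1 is not shown; dosing on days 1 and 5 of cycle 1 fits this). The next day 1 is day 29.
- Cohort A, last dose assumed on day 19: 29 − 19 = 10 days; with ±7 days, 3 to 17.
- Cohort B, last dose on day 21: 29 − 21 = 8 days; with ±7 days, 1 to 15.

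Across both cohorts the range is 1 to 17 days. Cycle 12 is closed by the end-of-study count, nominally also day 29.

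**Chance that a scheduled count catches one episode.** Assumption: a low count lasts L days, placed at random in the cycle. Detection = min(1, L/interval), with interval 28 days for day-1 counts and 7 days for weekly counts.

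| L (days) | Day-1 only | Weekly |
|---|---|---|
| 5 | 5/28 = 18% | 5/7 = 71% |
| 7 | 25% | 100% |
| 14 | 50% | 100% |

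If episodes follow dosing and resolve before the next day 1, day-1 detection is 0.

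**Effect on a 12-cycle incidence (illustration only).** Input: 26.3% grade 3/4 thrombocytopenia from the single-agent trial in Table 2-4. Assumptions: constant risk q per cycle, full detection in cycles 1–2, detection d in cycles 3–12, no unscheduled counts.
- q = 1 − (1 − 0.263)^(1/12) = 0.0251.
- Observed incidence = 1 − (1 − q)² (1 − dq)¹⁰.

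| d | Thrombocytopenia, true 26.3% | Neutropenia, true 31.6% (q = 0.0312) |
|---|---|---|
| 0 | 5.0% | 6.1% |
| 25% | 10.8% | 13.2% |
| 50% | 16.2% | 19.8% |
| 100% | 26.3% | 31.6% |

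In 30 patients, 26.3% is 30 × 0.263 = 7.9 patients with thrombocytopenia. The observed number would be 1.5, 3.2 or 4.9 at d = 0, 25% or 50%. If instead every affected patient has a first episode in cycles 1–2, patient-level incidence is not understated at all.

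**The case against.** Several points on the other side stand.

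- **No nadir data.** The documents give neither the timing nor the duration of cytopenia. Two passages point towards recovery in the off-week: Section 2.1.3 reports worse hematologic values on weekly than on alternate-week dosing, and Table 7-2 has a branch for grade 4 neutropenia that resolves within 7 days. Neither establishes it. A reader might infer that late counts are taken at recovery and that the safety profile is therefore definitely understated. The documents support only the direction, as likely.
- **Window and extra tests.** A cycle started early shortens or removes the drug-free week before the count, and unscheduled counts are allowed. However, an asymptomatic low count would not by itself prompt an extra test.
- **No trend is planned.** Section 13.1 promises incidences, not per-cycle rates. Worst grade per patient keeps the dense early data.
- **Size.** A reader might assume, say, a 3% risk per dosing week: over 24 dosing weeks that gives a true incidence of 52%, with 12–35% detected. That risk has no source in the documents. Solving the same model for 26.3% gives about 1.3% per dosing week and 5–16% detected. Even 26.3% comes from a weekly schedule in relapsed or refractory patients, and the constant-risk model ignores dose reductions and dropout.
- **Table 7-2.** A reader might call this a flat contradiction. The rule can also be read as telling sites what to do whenever toxicity is found, and two of its triggers (bleeding with grade 3 thrombocytopenia, febrile neutropenia) have clinical signs. What stands is that the rule's reach and the scheduled counts do not match from cycle 3.
- **Primary completion rate.** It is observed directly, and the accrual-suspension rule (Section 13.1.5) uses completion and non-hematologic toxicity. Neither is measured through these counts.

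**Conclusion.** The schedule facts are clear: weekly counts in cycles 1–2, then one scheduled count per cycle, nominally after a drug-free week, in 10 of 12 cycles. Sparse counts can miss transient low values and cannot add any, so late-onset and per-cycle hematologic toxicity in cycles 3–12 is likely understated. The size is unknown. The figures of 5.0–16.2% observed against 26.3% true show the scale only under constant risk per cycle, full detection in cycles 1–2, 0–50% detection afterwards and no unscheduled counts. Patient-level worst grade is less affected, and may not be affected if first episodes come early. The documents do not support saying that the primary safety result is wrong by a known amount, or that the completion analysis is biased. The point justifies an inexpensive change in reporting, so that a change in sampling is not read as a change in toxicity.

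**What to change.** In Section 13.1, add a table of CTCAE-graded hematologic laboratory toxicity taken from the collected CBC values, in two parts: cycles 1–2 (weekly counts) and cycles 3–12 (scheduled start-of-cycle counts, with unscheduled counts identified). State which cycle each start-of-cycle count is attributed to, since a day-1 count reflects dosing in the preceding cycle and the end-of-study count closes cycle 12. State that no conclusion about falling toxicity will be drawn across the break after cycle 2.

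Base the table on laboratory values rather than adverse event records. Sections 8.3, 8.3.1 and 12.1 limit recording to unexpected events of grade 3 or higher (and serious events). Section 8.3.1 counts an abnormal laboratory value as an adverse event only under further conditions. Cytopenias are already known effects of the drug (Section 2.1.3), so many could be absent from those records however often counts are taken.

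The cost is analysis wording, one extra table and smaller subsets in each part; no new data are needed.

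Separately, the count schedule in Table 8-1 and the any-time rule in Table 7-2 must be reconciled. How to do so is a clinical matter for the sponsor.
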